5.2 Subject Exclusion Criteria

Subjects meeting any of the following criteria at enrollment will be excluded from the study:

1. Known renal insufficiency from clinical history.
2. Use of systemic or intravaginal antibiotics* with potential activity against *N. gonorrhoeae* within 30 days prior to study drug administration. *Topical and intravaginal antifungals are permitted.
3. Use of systemic corticosteroid drugs or other immunosuppressive therapy within 30 days prior to enrollment.
4. Receipt or planned receipt of an investigational product in a clinical trial within 30 days prior to or 7 days after treatment administration.
5. Pregnant or breastfeeding.
6. Clinical diagnosis of pelvic inflammatory disease or genital ulcer.
7. Confirmed or suspected complicated or systemic gonococcal infection, such as abdominal pain, testicular pain, epididymitis, orchitis, arthritis, or endocarditis.
8. Receipt of magnesium/aluminum antacids, sucralfate, didanosine, or highly buffered drugs, within 6 hours before receipt of study drug.
9. Mutant *N. gonorrhoeae gyrA* serine 91 genotype from any anatomic site, as determined by the *gyrA* test assay on a specimen collected within 30 days of enrollment.
10. Known allergy or history of adverse reaction to ciprofloxacin.
11. Known allergy to quinolones.
12. Previous enrollment in this study.
13. Medical condition or other factor that in the judgment of the investigator might affect ability to comply with procedures.

5.3 Subject Withdrawal

5.3.1 Reasons for Withdrawal

Subjects may voluntarily withdraw their consent for further study participation at any time and for any reason, without penalty.

Refer to section 11 for how subjects who withdraw from study participation will be handled in study analyses.

Subjects may withdraw or be withdrawn from the study for any of the reasons given below. The reason for withdrawal will be recorded in the data collection form.

-
- Subject vomits within 1 hour of study medication administration.
 - Subject receives any systemic antibiotic other than the study medication prior to Visit 2 (Day 5-10).
 - Subject is pregnant or breastfeeding.
 - Discretionary decision by the site investigator.
 - At the discretion of the IRB, NIH, or other government agency as part of their duties to ensure that research subjects are protected.

5.3.2 Handling of Withdrawals

Subjects who withdraw voluntarily prior to receiving ciprofloxacin will be offered local standard of care treatment for *N. gonorrhoeae* and followed per clinic guidelines.

Subjects who withdraw voluntarily or never return after receiving ciprofloxacin and tolerated medication without difficulty will not be contacted for repeat gonorrhea testing or treatment.

Subjects who withdraw voluntarily or never return after being found to be positive for *N. gonorrhoeae* at Visit 2 (Day 5-10) will be contacted by phone and by certified mail with instructions that they should follow-up for treatment per local standard of care and should be followed per clinic guidelines.

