2.3 Potential Risks and Benefits

2.3.1 Potential Risks

Performance of the assay

Clinical specimens will be tested for a molecular marker of ciprofloxacin susceptibility. Treatment decisions will be made by the subject's clinician, per standard protocols, based on interpretation of laboratory results and selection of the best course of treatment based on available information. There is a small risk of a misclassification of susceptibility if the test were to show that the *N. gonorrhoeae* infection is ciprofloxacin-susceptible when in fact, it is resistant, and a subject with ciprofloxacin-resistant *N. gonorrhoeae* infection would not receive the appropriate treatment. The risk would be ameliorated if the test of cure visit (Visit 2, Day 5-10) displayed a treatment failure and the subject received standard treatment. The risk would therefore be that this would result in a delay of effective treatment.

The risk of a *N. gonorrhoeae* false negative test of cure result is estimated to be less than 0.5% and would result in inappropriate treatment for a subject with ciprofloxacin-resistant *N. gonorrhoeae* infection [9]. The risks of treatment failure include continued symptoms and potential transmission of *N. gonorrhoeae* to partners. Without effective re-treatment, treatment failure might result in complications including pelvic inflammatory disease, ectopic pregnancy,

infertility, chronic pelvic pain, and increased risk of transmission and HIV infection.

Risks from study procedures

Subjects may become embarrassed, worried, or anxious when discussing their sexual practices or ways for protecting against HIV and other infections passed during sex. They may also experience anxiety while they await test results. Women may expect to feel a little discomfort during the speculum exam. Subjects may experience gagging, discomfort, fainting, or bleeding when swabs are collected from the throat, rectum, urethra or cervix.

Risks of ciprofloxacin

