15. Once swabs have been collected, and all eligibility criteria have been assessed, subjects will receive one dose of ciprofloxacin 500 mg by mouth under direct observation with the date and time of administration documented.
 - Subjects will be observed for at least 5 minutes after administration of ciprofloxacin.
 - Subjects will be instructed to return to the clinic or to contact the study site coordinator immediately if they vomit within 1 hour of receiving study medication.
 - Subjects who vomit within 1 hour of study drug administration will be retreated for *N. gonorrhoeae* infection with an alternative recommended regimen per the local standard of care.
 16. Reminder to abstain from sexual intercourse or use condoms during any sexual contact until the Test of Cure Visit (Visit 2, Day 5-10) is complete
 17. Reminder to bring sex partners in for testing and treatment, if needed
 18. Reminder to return for Visit 2 (Day 5-10)

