7.3 Visit 3, Day 11 to 14 (Test of Cure Results)

1. Test results will be provided to subjects by phone call.
2. Subjects whose Visit 2 (Day 5-10) *N. gonorrhoeae* culture and NAAT results are negative will have completed participation in the study; no further follow-up is required.
3. Subjects who are *N. gonorrhoeae* culture positive or NAAT positive will be referred for standard of care treatment for *N. gonorrhoeae*.
4. Reminder to bring sex partners in for testing and treatment, if needed

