7.4 Unscheduled/Early Termination Visit

For an unscheduled visit at the subject's request or the site investigator's recommendation, subjects will have the following:

1. Interim medical history for assessment of specific symptoms that are potentially related to fluoroquinolone use as described in section 9, Assessment of Safety, and interim sexual history
2. Review of signs and symptoms at site of infection since the previous visit
3. Review of new antibiotics or concomitant medications contraindicated with ciprofloxacin
4. Targeted physical exam
5. Reminder to abstain from sexual intercourse or use condoms during any sexual contact until the Test of Cure Visit (Visit 2, Day 5-10) is complete
6. Reminder to bring sex partners in for testing and treatment, if needed
7. Reminder to return for follow-up visit

For an early termination visit, subjects will have the following:

1. Interim medical history for assessment of specific symptoms that are potentially related to fluoroquinolone use as described in section 9, Assessment of Safety, and interim sexual history
2. Review of signs and symptoms at site of infection since the previous visit
3. Review of new antibiotics or concomitant medications contraindicated with ciprofloxacin
4. Targeted physical exam
5. Reminder to bring sex partners in for testing and treatment, if needed

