11.4.3.1 Primary Analysis

The primary analysis will test whether the microbiological cure rate of ciprofloxacin in subjects infected with *gyrA* serine 91 genotype *N. gonorrhoeae* is greater than or equal to 95%. The cure rate will be estimated by the proportion of subjects infected with *gyrA* serine 91 genotype *N. gonorrhoeae* with microbiological cure at Visit 2 (Day 5-10).

Microbiological outcome status for the primary analysis is evaluated at Visit 2 (Day 5-10) and is defined as follows:

- Microbiological Cure: *N. gonorrhoeae* not detectable by culture from all anatomical sites that had detectable *N. gonorrhoeae* at Visit 1.

-
- Microbiological Failure: *N. gonorrhoeae* detectable by culture from at least one anatomical site that had detectable *N. gonorrhoeae* at Visit 1.
 - Non-evaluable: At least one of the following: Subject did not return for Visit 2 (Day 5-10), or culture results at Visit 2 (Day 5-10) were not available for any reason, or subject could not be evaluated for microbiological outcome status for any other reason.

For the PP analysis population, subjects with non-evaluable outcome status will be excluded from the analysis. For the micro-ITT and ITT analysis populations, subjects with non-evaluable outcome status will be included in analyses and classified as treatment failures. Subjects who discontinued early from the study due to a lack of treatment effect are included in all analysis populations as treatment failures.

The test will be performed by calculating the one-sided 95% modified Jeffreys confidence interval and comparing it to the value 0.95. The modification to the Jeffreys confidence interval was introduced in Brown, Cai, and DasGupta [18]. The lower bound of the confidence interval will be calculated as follows:

If the number of cures, denoted X , is less than the number of subjects included in the analysis, denoted N , then the lower bound of the one-sided 95% confidence interval is:

$$B(0.95; X + 0.5; N - X + 0.5)$$

where $B(\alpha; m_1; m_2)$ denotes the α quantile of a Beta(m_1, m_2) distribution.

If the number of cures is equal to the number of subjects included in the analysis, denoted N , then the lower bound of the one-sided 95% confidence interval is:

$$(0.05)^{1/N}$$

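### Treated subjects who silently miss the Visit 2 test of cure are not to be contacted for retesting or treatment, so the safeguard in section 2.3.1 does not reach them

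*Protocol*

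**What the plan says.** Section 2.3.1 discusses the risk that the assay calls a resistant infection susceptible. It says: "The risk would be ameliorated if the test of cure visit (Visit 2, Day 5-10) displayed a treatment failure" and the subject then received standard treatment. It also states the harm if that does not happen: "Without effective re-treatment, treatment failure might result in complications including pelvic inflammatory disease, ectopic pregnancy", with infertility and onward transmission also named.

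Section 5.3.2 sorts subjects who leave into three groups:

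- Those who withdraw before dosing are offered local standard treatment and followed under clinic guidelines.
- Those found positive at Visit 2 who then withdraw or do not come back "will be contacted by phone and by certified mail with instructions that they should follow-up for treatment per local standard of care".
- Those dosed who withdraw or "never return after receiving ciprofloxacin and tolerated medication without difficulty will not be contacted for repeat gonorrhea testing or treatment".

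SAP section 4.3 repeats the third rule in the present tense. For the analysis, section 11.4.3.1 excludes subjects without an evaluable outcome from the per-protocol (PP) population and adds: "For the micro-ITT and ITT analysis populations, subjects with non-evaluable outcome status will be included in analyses and classified as treatment failures".

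**The concern.** The third group has been given the study drug and has no post-treatment result, yet it is the only one of the three for which the plan describes no offer of care or outreach. The sentence treats a subject who simply misses a visit in the same way as one who has withdrawn, although the first has not refused contact.

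The safeguard in section 2.3.1 works only through a Visit 2 result. A failure in a subject who does not return, particularly one without symptoms, would not be found by any study procedure. What is at stake is mainly the subject's health and that of partners, through the complications that section 2.3.1 itself names.

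**Working it through.** **Does another provision close the gap?**

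- Section 7.1: subjects are reminded at Visit 1 to return, to abstain or use condoms, and to bring partners in. These steps precede any missed visit.
- Section 7.3: "Test results will be provided to subjects by phone call" at Visit 3. If Visit 2 was missed, there is no test-of-cure result to give.
- Section 7.4 and Appendix A: an unscheduled visit may follow the subject's request or the investigator's recommendation. Both it and the early-termination visit list history, symptom review and examination, but no culture or NAAT. A clinician may still test under local care.
- Section 14.6: assured care applies if the whole study is discontinued.

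Visit 2 is therefore the only visit after treatment with a scheduled gonorrhea test.

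**Plan's own figures (section 11.2).** Enrollment: 257 / (0.75 × 0.90) = 380.7, so 381 reproduces. Exact power at N = 257 and 98% cure is 85.4%, against the stated figure of about 85%. Neither is disputed; they supply the base for what follows.

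**Size of the gap.** Inputs: 381 enrolled, 25% culture negative at baseline, 98% cure (section 11.2). Non-return of 5% to 10% is an assumption.

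- Culture-positive subjects: 381 × 0.75 = 285.75, about 286.
- Non-returners: 285.75 × 0.05 = 14.3; 285.75 × 0.10 = 28.6, so 14 to 29.
- Expected undetected failures = non-returners × (1 − cure rate). Chance of at least one = 1 − cure rate^n, with n = 14 or 29.

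| Cure rate | Expected failures | Chance of at least one |
|---|---|---|
| 99% | 0.14 to 0.29 | 13% to 25% |
| 98% (planned) | 0.29 to 0.57 | 25% to 44% |
| 95% (the null boundary) | 0.71 to 1.43 | 51% to 77% |

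Applying the same rates to all 381 enrolled gives 19 to 38 subjects and, at 98%, 0.4 to 0.8 failures. That is on the high side if some culture-negative subjects were no longer infected.

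**Effect on the primary PP result.** As a deliberately pessimistic case, suppose 29 culture-positive non-returners were cured at only 90% and were added to 257 cured at 98%: (257 × 0.98 + 29 × 0.90) / 286 = 277.96 / 286 = 97.2%, against 98.0%.

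**The case against.** The strongest reply is that this is a deliberate and disclosed threshold: active pursuit is kept for subjects known to be positive. Section 2.3.1 is worded conditionally and states what may follow if a failure goes untreated. A reader might infer that sections 2.3.1 and 5.3.2 contradict each other, but because of that conditional wording they do not. What remains is that the mitigation covers fewer subjects than were treated.

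A reader might also infer that sites are barred from phoning someone who misses Visit 2, or that nobody would do so. The text does not support this. Never returning most naturally describes a final status, so section 5.3.2 does not rule out a call while the window is open. The Manual of Procedures, where such a step could sit, is not available here. The protocol and SAP describe no such call, but its absence in practice cannot be established. The rule does direct that, once the subject is treated as a non-returner, there is no outreach for retesting or treatment.

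Three further points stand in part:

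- Selection works against non-return: subjects must be available for follow-up (inclusion 7), and those judged unlikely to be able to comply can be excluded (exclusion 13). This lowers the number but does not protect those who still miss the visit.
- The 10% non-return case is high. Section 11.2 allows 10% for PP exclusions of every kind, so it assigns the whole allowance to one cause. Section 2.1 also cites more than 99% efficacy in susceptible infections before resistance spread, which favors the top row of the table.
- Certified mail about gonorrhea to people with no positive post-treatment test carries disclosure risk for a low expected yield. This is fair, and mail should be optional.

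**Conclusion.** The point holds as a patient-safety coverage gap. The plan states a rule, and the supplied documents contain no provision that brings a test of cure to the subjects it covers. It applies only to subjects who tolerated the dose, since those who vomit within an hour are retreated, and it does not deny care to anyone who comes back.

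The numbers are small: 14 to 29 subjects and about 0.3 to 0.6 expected undetected failures, given the assumed 5% to 10% non-return, the planned 25% culture-negative share and the planned 98% cure rate. Fewer than one failure is expected at the planned rate. The case for change rests on the seriousness of the listed harms and the low cost of the remedy.

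It would be wrong to infer that the primary conclusion is threatened. Non-returners are excluded from PP under a prespecified rule, and even the pessimistic case moves the rate by less than one percentage point. In micro-ITT and ITT they count as failures, which is conservative. An in-window call might recover some of those outcomes, but that is a side benefit.

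**What to change.** In section 5.3.2, limit the no-contact sentence to subjects who decline further contact, and make the same change to the copy in SAP section 4.3 so that the documents agree. For other treated subjects who miss Visit 2, attempt phone contact by the route the subject has agreed to. If the call falls within Day 5-10, its purpose is to complete Visit 2; after that, it is to advise retesting or care under the local standard. Certified mail can be left optional.

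If the no-contact rule is kept, section 2.3.1 should say that subjects who miss Visit 2 have no study test of cure.

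The cost is an amendment with IRB approval (section 14.2) and calls to treated non-returners whatever their baseline culture. At 5% to 10% of 381 that is about 19 to 38 subjects, or roughly 2 to 5 per site with eight sites (19/8 = 2.4; 38/8 = 4.8). No new study visit or test is needed, although advice to retest late may lead to some testing in local care. The downsides are a little site time and the confidentiality risk of phoning people about gonorrhea. Contact preferences should therefore be recorded at consent if they are not already; the consent pages are not in the copy reviewed.

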5.3.2.1 Termination of Study

Although the study sponsor has every intention of completing the study, the sponsor reserves the right to terminate the study at any time for clinical or administrative reasons. Reasons for termination include, but are not limited to, study closure at the discretion of DMID.

6 GYRASE A ASSAY/STUDY TREATMENT

6.1 Gyrase A Assay Description

Real-time PCR testing protocol: The laboratories participating in this study will follow the testing protocol as described in Siedner et al [15] with modifications. For real-time PCR analysis of the *gyrA* gene, remnant specimens will be subject to nucleic acid (DNA) extraction by using automated nucleic acid extraction utilizing either the bioMerieux easyMag, or the Qiagen EZ1, or Qiacube platforms, as determined in the optimization studies. Extracted samples will be used for real-time PCR. Amplification and melting-curve analysis of specimens will be performed by using a Roche LightCycler 480 or LightCycler 2.0 platforms (Roche Diagnostics, Pleasanton, CA). Amplified regions of the *gyrA* gene will be assessed for mutations in the Ser 91 codon through use of melting-curve analysis with probes specific to that region of the *gyrA* gene. The probes for the serine 91 amplicon (*gyrA*-ser-Flu and *gyrA*-ser-LC) are a paired set of FRET probes, including a LightCycler Red640 probe and a fluorescein-labeled probe, separated by 1 bp. The Red640 oligonucleotide has a maximal absorption and emissions of 622 and 638 nm, respectively. Amplification of PCR product will be followed by melt-curve analysis to confirm specificity of amplification and genotype. Melting-curve analysis will be performed by using LightCycler software (v.4.0). The software will be used to plot the negative value of the first derivative of fluorescence per unit time to distinguish peak melting temperatures from melting-curve plots. Designation of predicted susceptibility is based upon the observed melting curve parameters as previously described [15].

6.2 Ciprofloxacin Description

Ciprofloxacin is a quinolone medication approved by the FDA for the treatment of gonorrhea. Ciprofloxacin hydrochloride, USP, a fluoroquinolone, is the monohydrochloride monohydrate salt of 1- cyclopropyl-6-fluoro-1, 4-dihydro-4-oxo-7-(1piperazinyl)-3-quinolinecarboxylic acid. The molecular weight of the ciprofloxacin hydrochloride monohydrate is 385.82. It is a faintly yellowish to light yellow crystalline substance.

6.2.1 Ciprofloxacin Formulation

Ciprofloxacin 500 mg tablets

6.2.2 Ciprofloxacin Acquisition

Ciprofloxacin will be purchased centrally, and upon request by DMID, will be transferred to the following address:

DMID Clinical Agents Repository (CAR)
XXXXXXXXXX

Ciprofloxacin will be shipped from the DMID CAR to the study site upon request and approval by DMID.

6.2.3 Storage and Stability

Ciprofloxacin is stable at room temperature. Stability of this medication will be maintained by storing the drug below 30°C (86°F). The storage room temperature will be monitored on business days.

6.2.4 Dosage Preparation and Administration

Ciprofloxacin tablets will be administered orally and can be taken with or without food. Subjects will receive 500mg and will be directly observed.

6.2.5 Accountability Procedures

Fisher repository will ship packaged ciprofloxacin to the investigational sites. At each site, medication packages will be kept in a locked storage cabinet at the clinic and administered by the study personnel. Accountability records will be maintained by designated site staff (i.e., study personnel or pharmacy staff). Unused study treatment will be destroyed or returned to Fisher BioServices at the end of the study. Unused study treatment will not be destroyed without DMID approval.

6.2.6 Assessment of Subject Compliance

Medication will be given and directly observed by the study staff and recorded in the subject's case report form (CRF). Since medication will be directly observed, there will be no need for return of study medication packaging or a medication diary at the follow-up visit.

6.2.7 Concomitant Medications

Administration of any contraindicated medications or new antibiotics after enrollment will be recorded on the appropriate data collection form. Contraindicated medications will include all medications contraindicated with ciprofloxacin (described in section 5.2) taken 30 days prior to signing the informed consent form through Visit 2 or early termination, whichever occurs first.

Subjects who have received study medication and are subsequently diagnosed with a concomitant infection, which requires systemic antibiotics will receive treatment according to the local clinic's standard of care.

Use of new medication should prompt evaluation for the presence of a new diagnosis of chronic medical disease or condition.

Oral contraceptives are allowed, as they do not alter the metabolism of ciprofloxacin.

7 STUDY SCHEDULE

Complete study schedule details listed by study visit day are described below. Refer also to Appendix A.

7.1 Visit 1, Day 1 (Screening/Enrollment)

Screening and enrollment will occur at the same clinic visit. Potential subjects will be informed about the study and invited to participate. Subjects who are interested in the study will be asked to sign a consent form that will describe the purpose of the study, the procedures to be followed, the risks and benefits of participating, and will include a separate section for consent to store samples for future use. A copy of the consent form will be given to the subject and this fact will be documented in the CRF.

The following will be performed for subjects who give informed consent:

1. Demographic information including age, sex, and gender will be collected from the subject
2. Eligibility criteria will be reviewed with the subject
3. Discuss pertinent medical history for assessment of specific symptoms that are potentially related to fluoroquinolone use as described in section 9, Assessment of Safety, and sexual history will be obtained by interview of subjects to assure eligibility. Concomitant infections will be reviewed.
4. Review of signs and symptoms within the past 7 days
5. All new antibiotics or concomitant medications contraindicated with ciprofloxacin taken in the 30 days prior to signing the informed consent will be recorded on the appropriate data collection form
6. Targeted physical exam
7. Speculum exam for females
Note: Women diagnosed with BV by local standard test at Visit 1 will receive treatment for BV at Visit 2 according to local standard of care.
8. Urine pregnancy test for females of childbearing potential
9. One swab for *N. gonorrhoeae* culture and one swab for NAAT and *gyrA* serine 91 genotype from the throat*
10. One swab for *N. gonorrhoeae* culture and one swab for NAAT and *gyrA* serine 91 genotype from the rectum*
11. One swab for *N. gonorrhoeae* culture from the urethra (males)*
12. Urine specimen for NAAT and *gyrA* serine 91 genotype (males)*
13. Cervical swab for *N. gonorrhoeae* culture (females)*
14. Cervical or vaginal swab for NAAT and *gyrA* serine 91 genotype (females)*
*Note 1: Only at the suspected infected anatomical site based on prior test results or other sites as clinically indicated
*Note 2: *GyrA* assay is required only if NAAT is positive

-
15. Once swabs have been collected, and all eligibility criteria have been assessed, subjects will receive one dose of ciprofloxacin 500 mg by mouth under direct observation with the date and time of administration documented.
 - Subjects will be observed for at least 5 minutes after administration of ciprofloxacin.
 - Subjects will be instructed to return to the clinic or to contact the study site coordinator immediately if they vomit within 1 hour of receiving study medication.
 - Subjects who vomit within 1 hour of study drug administration will be retreated for *N. gonorrhoeae* infection with an alternative recommended regimen per the local standard of care.
 16. Reminder to abstain from sexual intercourse or use condoms during any sexual contact until the Test of Cure Visit (Visit 2, Day 5-10) is complete
 17. Reminder to bring sex partners in for testing and treatment, if needed
 18. Reminder to return for Visit 2 (Day 5-10)

